## **8.0 Research Question and Objectives**

### **8.1 Research Question**

What is the effectiveness and the influence of adherence on treatment outcome of the interferon-free ABBVIE REGIMEN ± RBV in patients with CHC in a real life setting across clinical practice patient populations?

### **8.2 Objectives**

#### **8.2.1 Primary Objective**

1. To describe in routine clinical practice the effectiveness of the interferon-free ABBVIE REGIMEN ± RBV in patients with CHC as evidenced by SVR12

#### **8.2.2 Secondary Objectives**

2. To provide real world evidence for predictive factors of virological response
3. To describe the pattern of real world use of the ABBVIE REGIMEN ± RBV with respect to different patient and treatment characteristics

---

Confidential Information

No use or disclose outside AbbVie is permitted without prior written authorization from AbbVie

4. To evaluate the influence of adherence on treatment outcome in routine clinical practice
5. To evaluate the contribution of the patient support program (PSP) to disease control, treatment continuation over time, patient satisfaction and PSP utilization
6. To assess viral resistance patterns

## **9.0      Research Methods**

### **9.1      Study Design**

This is a prospective, multi-center observational study in patients receiving the interferon-free ABBVIE REGIMEN with or without RBV. The prescription of a treatment regimen is at the discretion of the physician in accordance with local clinical practice and label, is made independently from this observational study and precedes the decision to offer the patient the opportunity to participate in this study.

Adult patients chronically infected with HCV, receiving the interferon-free ABBVIE REGIMEN will be offered the opportunity to participate in this study during a routine clinical visit at the participating sites.

[figure not shown]
After written informed consent has been obtained, patient data including demographic data, HCV disease characteristics, co-morbidities, co-medication, treatment details, and laboratory assessments as recorded in the patient's medical records (source documentation) will be documented in the electronic case report form (eCRF). Patients will be observed for the duration of the ABBVIE REGIMEN therapy and for up to 24 weeks after treatment completion. No patient identifiable information will be captured, a unique patient number will be automatically allocated by the web based eCRF system once the investigator or designee creates a new patient file.

This study is focusing on collecting real-world data. Follow-up visits, treatment, procedures and diagnostic methods will follow physicians' routine clinical practice. The observational study period entails the following data collection schemes, data documented will be those closest to the time windows as indicated in Figure 1:

- 12-week treatment regimen: four visits plus two interim data collection windows
- 24-week treatment regimen: four visits plus three interim data collection windows

This schedule is based on the anticipated regular follow-up for patients undergoing treatment for CHC.

Figure 1 - Study Flowchart

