## 9.7 Data Analysis

### 9.7.1 Analysis Population, Time Windows and Handling of Missing Data

The target population (TP) is defined as all patients who fulfill the criteria specified in Section 9.2.1. The core population (CP) is defined as all patients of the TP, who have started the treatment combination recommended in the current local label for their disease characteristics. Patients not receiving the treatment recommended in the local label will be summarized in the non-core population (NCP). In addition, the core population with sufficient follow-up data (CPSFU) is defined as all CP patients, who fulfil one of the following criteria:

- (1) evaluable HCV RNA data  $\geq 70$  days after the last actual dose of the ABBVIE REGIMEN (i.e. data within the SVR12 time window)
- (2) a HCV RNA value  $\geq 50$  IU/mL at the last measurement post-baseline (i.e. no virological response achieved at the last measurement on-treatment or post-treatment)
- (3) HCV RNA  $< 50$  IU/mL at the last measurement post-baseline, but no HCV RNA measurement  $\geq 70$  days after the last actual dose of the ABBVIE REGIMEN due to reasons related to safety (e.g. dropped out due to AE) or incomplete efficacy information (e.g. virologic failure such as relapse is reported in the eCRF but date and value of the corresponding HCV RNA test is missing). This means only patients who had virological response at their last on-treatment or post-treatment measurement, but had no HCV RNA measurements  $\geq 70$  days post-treatment for reasons not related to safety or effectiveness (e.g. lost-to-follow-up or patient not willing to perform an additional HCV RNA test  $\geq 70$  days post-treatment) will be excluded from this analysis.

The Safety Population (SP) is defined as all patients who received at least one dose of the ABBVIE REGIMEN.

In accordance with the non-interventional nature of the study all HCV RNA measurements will be performed at the sole discretion of the physician and all HCV RNA measurements have to be entered into the eCRF. All recorded HCV RNA values will be assigned to appropriate time points (baseline, on-treatment visits, EoT visit, post-

---

Confidential Information

No use or disclose outside AbbVie is permitted without prior written authorization from AbbVie

---

treatment visits). The time windows for the assignments will be specified in the statistical analysis plan (SAP).

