## Annex 3. Patient Support Program (PSP) Utilization Questionnaire

12 weeks treatment: At Interim early post-treatment visit  
24 weeks treatment: At Interim mid treatment visit and Interim early post-treatment visit

Since the last visit, have you utilized any components from the AbbVie Patient Support Program?

No

Please ignore questions below and return questionnaire to your physician or study nurse

Yes

Please specify service(s) used:

●  Personal support (e.g. Care Coach)

▲  Educational and information material (e.g. magazines, leaflets, diaries)

✖  Printed

Please specify how often used:  Usually daily  
 Several times per week  
 Usually once weekly  
 Less than once weekly

✚  Online

Please specify how often used:  Usually daily  
 Several times per week  
 Usually once weekly  
 Less than once weekly

■  Additional digital and mobile resources

★  Web-portal

Please specify how often used:  Usually daily  
 Several times per week  
 Usually once weekly  
 Less than once weekly

○  App

Please specify how often used:  Usually daily  
 Several times per week  
 Usually once weekly  
 Less than once weekly

●  Reminders

♥  Other

Confidential Information

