## Annex 4. Patient Support Program (PSP) Utilization and Satisfaction Questionnaire

12 weeks treatment: At Interim early on-treatment visit, week 12 EoT visit and SVR 12 visit

24 weeks treatment: At Interim early on-treatment visit, week 24 EoT visit and SVR 12 visit

Since the last visit, have you utilized any components from the AbbVie Patient Support Program?

No

→ Please ignore questions below and return questionnaire to your physician or study nurse

Yes

→ What is your level of satisfaction of the AbbVie Patient Support Program in general?

- Very good
- Good
- Satisfactory
- Poor

→ Did the Program address your needs?  Yes, fully  Yes, mostly  No

↓ Please specify service(s) used:

- Personal support (e.g. Care Coach)

→ Please specify your level of satisfaction:  Very good  
 Good  
 Satisfactory  
 Poor

- ▲  Educational and information material (e.g. magazines, leaflets, diaries)

- ✖  Printed

→ Please specify how often used:  Usually daily  
 Several times per week  
 Usually once weekly  
 Less than once weekly

→ Please specify your level of satisfaction:  Very good  
 Good  
 Satisfactory  
 Poor

- ✚  Online

→ Please specify how often used:  Usually daily  
 Several times per week  
 Usually once weekly  
 Less than once weekly

→ Please specify your level of satisfaction:  Very good  
 Good  
 Satisfactory  
 Poor

Confidential Information

■  Additional digital and mobile resources

★  Web-portal

- Please specify how often used:  Usually daily  
 Several times per week  
 Usually once weekly  
 Less than once weekly

- Please specify your level of satisfaction:  Very good  
 Good  
 Satisfactory  
 Poor

○  App

- Please specify how often used:  Usually daily  
 Several times per week  
 Usually once weekly  
 Less than once weekly

- Please specify your level of satisfaction:  Very good  
 Good  
 Satisfactory  
 Not satisfactory

●  Reminders

- Please specify your level of satisfaction:  Very good  
 Good  
 Satisfactory  
 Poor

●  Other

- Please specify your level of satisfaction:  Very good  
 Good  
 Satisfactory  
 Poor

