3. STUDY DESIGN

3.1 Overview of Study Design and Dosing Regimen

This is a prospective, multi-center observational study in adult patients chronically infected with HCV receiving the interferon-free ABBVIE REGIMEN ± RBV.

University centers and outpatient clinics qualified by training and experience in the management of patients with CHC participate in this study.

The prescription of a treatment regimen is at the discretion of the physician in accordance with local clinical practice and label, is made independently from this observational study and precedes the decision to offer the patient the opportunity to participate in this study.

After written informed consent has been obtained, patient data including demographic data, HCV disease characteristics, co-morbidities, co-medication, treatment details, and laboratory assessments as recorded in the patient's medical records (source documentation) are documented in the electronic case report form (eCRF). Patients are observed for the duration of the ABBVIE REGIMEN therapy and for up to 24 weeks after treatment completion.

[figure not shown]
The observational period for patients receiving 12 weeks of ABBVIE REGIMEN is max. 36 weeks (12 weeks treatment and 24 weeks post-treatment observation) and for patients receiving 24 weeks of ABBVIE REGIMEN the observational period is max. 48 weeks (24 weeks treatment and 24 weeks post-treatment observation).

Follow-up visits, treatment, procedures and diagnostic methods follow physicians' routine clinical practice. The observational study period entails the following data collection schemes, data documented are those closest to the time windows as indicated in Figure 1:

- 12-week treatment regimen: four visits plus two interim data collection windows
- 24-week treatment regimen: four visits plus three interim data collection windows

This schedule is based on the anticipated regular follow-up for patients undergoing treatment for CHC.

Figure 1 - Study Flowchart

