4.2.8.4 Laboratory Data

All reported clinical laboratory test results will be assigned to one of the time points using the time windows specified in the Table 4. All will be performed for the SP by treatment regimen and cirrhosis status.

Changes from baseline to each post-baseline visit will be summarized descriptively (N, mean, SD, median, minimum, maximum). A summary table will show laboratory hematology. In another table information about clinical chemistry

In a further table CD4 and HIV-RNA are displayed for patients with HIV only by visit. A further table will show the viral resistance.

Instead of the shift tables mentioned in the study protocol, the number and percentage of subjects with post-baseline values until EoT meeting the specified criteria for Potentially Clinically Significant (PCS) laboratory values (defined in Table 10) will be summarized. A post-baseline value must be more extreme than the baseline value to be considered a PCS finding.

Table 10 Criteria for PCS laboratory values

Laboratory data	Very Low	Very High
Laboratory hematology		
Hemoglobin [g/L]	<80	
Platelets [10^9 /L]	<50	
Laboratory clinical chemistry		
ALT		>5 x ULN and >= 2 x baseline
AST		>5 x ULN and >= 2 x baseline
Creatinine [$\mu\text{mol}/\text{L}$]		>132.605
Creatinine clearance [mL/min]***	<50	

*** estimated by Cockcroft-Gault-Formula (see above)

Additionally, for hemoglobin and creatinine clearance, the number and percentage of subjects with a maximum Common Terminology Criteria for Adverse Events (CTCAE) Grade of 0, 1, 2, 3, or 4 (see definitions in Table 11) at any post-baseline visit (regardless of the baseline value) through the end of treatment (i.e., Final Treatment Value) will be summarized. For the liver function tests (LFTs) of ALT and AST, the number and percentage of subjects in with a maximum CTCAE Grade of 0, 1, 2, 3, or 4 (see definitions in Table 11) at any post-nadir visit through the end of treatment (i.e., Final Treatment Value) will be summarized. Note, for these analyses, the nadir is used for reference (including baseline).

Table 11 Definition of CTCAE Grades 0-4

Laboratory data	Grade 0	Grade 1	Grade 2	Grade 3	Grade 4
ALT	<=ULN	>ULN – 3 x ULN	> 3 – 5 x ULN	> 5 – 20 x ULN	> 20 x ULN
AST	<=ULN	>ULN – 3 x ULN	> 3 – 5 x ULN	> 5 – 20 x ULN	> 20 x ULN
Hemoglobin Decreased [g/L]	>=130	<130 – 100	< 100 - 80	< 80 - 65	< 65

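### The instruction to document values closest to the Figure 1 windows is not reconciled with the worst-value laboratory tables in SAP 4.2.8.4, nor in wording with the rule to enter every HCV RNA result

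*Protocol*

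**What the plan says.** **Collection rule.** Protocol 9.1 states that "data documented will be those closest to the time windows as indicated in Figure 1". SAP 3.1 has the same rule: "data documented are those closest to the time windows as indicated in Figure 1". Protocol 9.2 points the reader to 9.1, 9.4.1 and Figure 1 for the documentation schedule.

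**Collection points.** Protocol 9.1 gives "12-week treatment regimen: four visits plus two interim data collection windows" and "24-week treatment regimen: four visits plus three interim data collection windows". The interim points are named in the questionnaire annexes. Annex 4 has "12 weeks treatment: At Interim early on-treatment visit, week 12 EoT visit and SVR 12 visit" and Annex 3 has "24 weeks treatment: At Interim mid treatment visit and Interim early post-treatment visit".

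**HCV RNA.** Protocol 9.7.1 requires that "all HCV RNA measurements have to be entered into the eCRF". SAP 4.2.2 carries the same sentence.

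**Chemistry and hematology.** Protocol 9.6.1 has routine laboratory assessments transcribed, but confines eCRF entry to what the protocol specifies. Protocol 9.7.4 and SAP 4.2.8.4 allocate reported results to time windows without saying which results must be reported.

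**Use of the laboratory data.** SAP 4.2.8.4 tabulates the maximum CTCAE grade of hemoglobin and creatinine clearance "at any post-baseline visit (regardless of the baseline value) through the end of treatment". It does the same for ALT and AST after the nadir. It replaces the protocol's shift tables with counts of PCS values up to EoT.

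**The concern.** Two instructions on data entry stand side by side. One selects values by their nearness to a window; the other, for HCV RNA, takes everything. A site has to guess which applies to a result that lies between windows.

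For laboratory safety data the guess matters, because the SAP summarizes extremes. A draw taken between scheduled points, for instance because of symptoms, is the kind least likely to be closest to a window and quite likely to hold the extreme. Protocol 7.1 describes on-treatment ALT rises as short-lived and mostly settling while therapy continues, a pattern that a few selected values can miss. At stake are the PCS and CTCAE rates in the safety population, and their comparability between sites that read 9.1 differently.

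**Working it through.** The plan gives no figure for this point, so the check sets the passages against each other, counts collection points and adds two illustrations.

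**1. Collection points.** A 12-week course has 4 + 2 = 6; a 24-week course has 4 + 3 = 7. By Annexes 3 and 4, one interim point is early post-treatment. The post-baseline on-treatment points are then 2 for 12 weeks (early on-treatment, EoT) and 3 for 24 weeks (early, mid, EoT). This is inferred from questionnaire schedules, because Figure 1 is not shown.

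**2. Analysis windows.** The weekly laboratory windows are week 4 (days 15–42), week 8 (43–70), week 12 (71–98) and week 16 (99–126), as printed in Protocol Table 4. The SAP's EoT window runs from 28 days before to 7 days after the last dose.
- Last dose on day 84: the EoT window is days 56 to 91 (84 − 28, 84 + 7). Weeks 4, 8 and 12 open before the last dose, so there are three weekly windows plus EoT for two collected sets.
- Last dose on day 168: the EoT window is days 140 to 175. Weeks 4, 8, 12 and 16 open before the last dose, so there are four weekly windows plus EoT for three collected sets.

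Taken literally, the 9.1 scheme does not fill all these windows.

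**3. Direction.** With baseline fixed, the worst of a subset cannot be worse than the worst of the full set. Omitting results can therefore only lower, or leave unchanged, the PCS counts and the maximum grades of hemoglobin and creatinine clearance. For ALT and AST after the nadir, a missed peak also lowers the grade. If the omitted result is the nadir itself, however, the reference point moves and the grade can shift either way.

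**4. Illustration A: share of extremes missed.** Assume *m* routine on-treatment draws, *k* of them entered, and the extreme equally likely at any draw. Then the share missed = 1 − *k*/*m*.
- 12 weeks, *k* = 2: 0% (*m* = 2), 33% (*m* = 3), 50% (*m* = 4), 67% (*m* = 6).
- 24 weeks, *k* = 3: 0% (*m* = 3), 25% (*m* = 4), 50% (*m* = 6).

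**5. Illustration B: transient rise in a 12-week course.** Assume onset *s* uniform over weeks 1 to 10 (a 9-week range), duration *d* weeks, and values entered at weeks 4 and 12 only. A rise is captured if the interval from *s* to *s* + *d* covers an entered week.
- *d* = 2: *s* from 2 to 4, so 2/9 = 22%.
- *d* = 3: *s* from 1 to 4 or 9 to 10, so (3 + 1)/9 = 44%.
- *d* = 4: *s* from 1 to 4 or 8 to 10, so (3 + 2)/9 = 56%.

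With draws at weeks 4, 8 and 12, all entered, capture is 4/9, 7/9 and 9/9. With two-weekly draws, all entered, it is 100% by construction, since every rise lasts at least as long as the gap between draws.

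| Duration (weeks) | Entered at 4 and 12 | All four-weekly draws | Gap (points) | All two-weekly draws | Gap (points) |
|---|---|---|---|---|---|
| 2 | 22% | 44% | 22 | 100% | 78 |
| 3 | 44% | 78% | 33 | 100% | 56 |
| 4 | 56% | 100% | 44 | 100% | 44 |

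If routine draws fall only at weeks 4 and 12, the gap is zero. Draw frequency, onset and duration are all assumptions; the documents give none of them.

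**6. HCV RNA.** Take a negative result on day 80 after the last dose and a positive one on day 120. Under 9.1 alone a site might enter only the day 80 value. Under 9.7.1 and SAP 4.2.2 it must enter both. The second rule names the variable and is mandatory, so it governs, and the loss under it is zero.

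**The case against.** A reader might infer that breakthroughs and relapses go unrecorded and that SVR12 suffers. The documents do not support this: the all-values rule for HCV RNA appears in both, and the missing-data rules in Protocol 9.7.1 presuppose it, since they draw on values outside a window. What remains is that the rule stands in the analysis sections and is not repeated in 9.1 or 9.4.1, where a site looks for its instructions.

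A reader might also take 9.1 to forbid entry of anything else. It does not contain the word *only*. Protocol 9.1 also speaks of laboratory assessments as found in the medical records, 9.4.1 of what the charts hold, and 9.6.1 of transcribing routine assessments. Table 2 lists on-treatment visits in the plural, and the weekly laboratory windows suggest that more than two sets were expected. All of this stands, and it means that loss is a risk rather than an established fact. It does not amount to an instruction to enter every laboratory result.

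Abnormal laboratory findings can be reported as adverse events at any time (Protocol 9.7.6 and 11.1), and ribavirin dose changes for anemia are tabulated. This mitigates the problem in part, but an adverse event entry need not supply the number from which a CTCAE grade or PCS flag is derived.

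Finally, 9.1 says that the schedule reflects expected routine follow-up, and the CTCAE text grades by visit. If routine draws match the scheme, nothing is lost. That is correct, and it is why no single loss figure can be given.

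**Conclusion.** The point holds for chemistry and hematology. No explicit rule overrides 9.1 for these data, while SAP 4.2.8.4 relies on extremes through EoT. If sites apply 9.1 literally, PCS and worst-grade rates can be biased downward and can vary between sites for reasons unrelated to patients. The size runs from zero, when draws coincide with the scheme, to 67% of extremes missed with six draws and two entered in a 12-week course. It rests on an unstated draw frequency and on a count of on-treatment points inferred without Figure 1.

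For HCV RNA the finding is only a contradiction in wording. The primary endpoint, the breakthrough and relapse definitions and the sample size are not affected.

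**What to change.** In Protocol 9.1 and SAP 3.1, confine the closest-to-window rule to choosing a value for by-visit summaries. Repeat the all-HCV-RNA rule in 9.1 and 9.4.1 and in SAP 3.1.

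State that all available on-treatment results through EoT are entered for the parameters behind SAP Tables 10 and 11: ALT, AST, hemoglobin, platelets and creatinine (from which creatinine clearance is calculated). State that all of them feed the PCS and CTCAE tables. If that is too much transcription, add the worst on-treatment value and its date for each parameter to the EoT page. If neither is done, label those tables as based on documented values only.

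The cost is wording and some extra transcription of results already in the chart, plus an added eCRF field if the EoT-page option is chosen. No test or visit is added.

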## 9.2 Setting

For overall research design and observational documentation schedule refer to Sections 9.1 and 9.4.1 as well as to Figure 1.

### 9.2.1 Target Population

Patients are eligible for observation in this cohort if the following applies:

- Treatment-naïve or -experienced adult male or female patients with confirmed CHC, genotype 1 or 4, receiving combination therapy with the interferon-free ABBVIE REGIMEN ± RBV according to standard of care and in line with the current local label
- If RBV is co-administered with the ABBVIE REGIMEN, it has been prescribed in line with the current local label (with special attention to contraception requirements and contraindication during pregnancy)
- Patients must voluntarily sign and date an informed consent prior to inclusion into the study
- Patient must not be participating or intending to participate in a concurrent interventional therapeutic trial

Confidential Information

No use or disclose outside AbbVie is permitted without prior written authorization from AbbVie  
Core Protocol Version 3.0 – Belgium Version 2.0 (9 June 2015) Page 22 of 58

## 9.2.2 Study Duration

This is a prospective, observational study. The inclusion period will be approximately 24 months and the observational period of the study will be from baseline visit until 24 weeks post-treatment.

The observational period for patients receiving 12 weeks of ABBVIE REGIMEN will be max. 36 weeks (12 weeks treatment and 24 weeks post-treatment observation) and for patients receiving 24 weeks of ABBVIE REGIMEN the observational period will be max. 48 weeks (24 weeks treatment and 24 weeks post-treatment observation).

